3.2 Study Design

This is a two-arm, randomized (1:1), parallel, nationwide open-label non-inferiority clinical trial. Only the assessment of the primary outcome is blinded. Randomization was stratified by C-reactive protein (< 35 vs ≥ 35 mg/L). Patients are followed up until the 12-month follow-up visit (which can take place between 11 and 14 months after randomization), although the primary outcome is defined at the 6-month follow-up visit (which can take place between 5 and 9 months after randomization). Outcomes are defined by the medical examinations at the two planned visits (6 or 12 months), clinical examinations during the course of the disease and via self-reported (electronic) questionnaires, filled in by the patients or their parents. The questionnaires provide daily and weekly patient reported outcomes.

4 Statistical Hypotheses

The null hypothesis to be tested in relation to the primary estimand (detailed in Sec. 3.1.1) is as follows:

- **Null hypothesis:** the risk of having sequelae 6 months after BJI is **at least** 5% higher when initiating high-dose OT than when initiating IVT ². Formally, $\mathcal{H}_0 : \pi_1 - \pi_0 \geq 5\%$, where π_1 and π_0 are the 6 months risk when initiating high-dose OT and IVT, respectively.

versus

- **Alternative hypothesis:** the risk of having sequelae 6 months after initiating BJI is **at most** 5% larger when initiating high-dose OT than when initiating IVT. Formally, $\mathcal{H}_1 : \pi_1 - \pi_0 < 5\%$.

²As for the definition of the estimand, it is the risk regardless of initiation of any additional interventions during the 6 months follow-up, including switching treatment (from OT to IVT or the other way around), when needed to ensure good clinical care.

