6.1 Primary Endpoint Analysis

6.1.1 Main Analytical Approach

For this analysis we will use the “Main analysis set” detailed in Section 5. We will estimate the primary estimand, that is, the difference in risk $\pi_1 - \pi_0$, as the empirical (i.e. observed) proportion of participants with sequelae after 6 months in the high-dose OT intervention group minus the same proportion in the IVT intervention group. An appropriate one-sided 97.5% confidence interval and a matching p-value for the null hypothesis $\mathcal{H}_0 : \pi_1 - \pi_0 \geq 5\%$ will be computed using an exact

unconditional test. An exact approach will be used instead of alternatives based on (asymptotic) normal approximations, because the expected number of events in each group are very low (say, 0 or 1) and thus usual (asymptotic) approximations do not seem reliable. Specifically, we will use an exact unconditional test using the score statistic ordering, as implemented in the function `uncondExact2x2` of the R package `exact2x2`; see [4] for the mathematical details and Appendix 8.1 for the specific R code that we will use. The score statistic ordering was chosen for its good power properties, as compared to alternatives [4].

If the upper limit of the 97.5% confidence interval of the risk difference $\pi_1 - \pi_0$ does not include the non-inferiority margin 5% or, equivalently, if the matching p-value is less than 2.5%, we will reject the null hypothesis³.

In addition, we will report the estimates of the risk in each group (i.e. the empirical proportions) together with exact binomial two-sided 95% confidence intervals (computed using the `binom.test()` function of R).

Note that the above statistical analyses will ignore that the randomization was stratified by C-reactive protein (< 35 vs ≥ 35). This is usually not recommended, as this usually leads to a decrease in power [5, 8]. However, our context is very specific, as we expect close to zero sequelae in each group (whatever the C-reactive protein level). This has two important consequences. First, the loss of power is expected to be non-existent or negligible. Second, ensuring proper type-I error control using a “covariate-adjusted” alternative approach seems difficult using standard software.

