6.2 Secondary Endpoints Analyses

The main statistical analysis for the secondary outcomes and estimands defined in Section 3.1.2 will be similar to that of the primary outcome defined in Section 6.1.1, except that:

- we will compute a two-sided 95%-CI instead of a one-sided 97.5%-CI and we will not compute an accompanying p-value (see appendix 8.3 for the specific R code that we will use).
- we will use the “Secondary outcomes analysis set” instead of the “Main analysis set” (see details of the sets in Section 5).

The change of analysis set is because we want to use as much data as possible for the analyses and because we cannot think of any reason why a missing follow-up at 6 months (i.e., a missing primary outcome) should lead to excluding a patient for the secondary outcome analyses. For the same reason, we will proceed similarly for the tertiary (safety and exploratory) outcomes (see section 6.3).

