We prespecify the analysis sets and the statistical methods that will be used to analyze each of the above Safety and Exploratory outcomes as follows. Additional (post hoc) exploratory analyses might be performed.

Analysis sets. For the analyses of outcomes S1, S2, S3 and E7 we will use the "All participants analysis set", whereas we will use the "Secondary outcomes analysis set" for outcomes E1–E2 and E5–E6 and E8–E9 and the "Long-term outcomes analysis set" for outcomes E3–E4. This information is summarized in Table 6.3.

Outcome	Analysis set				
	“Main”	“Second”	“All”	“Late”	“PS”
Primary	X				X
S1			X		
S2			X		
S3			X		
E1		X			
E2		X			
E3				X	
E4				X	
E5		X			
E6		X			
E7			X		
E8		X			
E9	X				

Note: “Main”, “Second”, “All”, “Late” & “PS” stand for “Main analysis set”, “Secondary outcomes analysis set”, “All participants analysis set”, “Long-term outcomes analysis set” and “Principal stratum analysis set”.

Table 1: Analysis sets for each outcome.

Binary outcomes analyses (B). Outcomes S1–S3, E3–E7 are binary outcomes. They will be analyzed using the same statistical method as for the primary outcome, except that we will compute a two-sided 95% CI instead of a one-sided 97.5% and that no p-value will be computed (see appendix 8.3 for the specific R code that we will use).

Time-to-event analyses (TTE). Outcomes S1–S3, E1–E2 and E6–E9 are –or can also be analyzed as– time to event outcomes. They will be analyzed by estimating (and plotting) the cumulative incidence/risk function within each treatment arm, with pointwise two-sided 95%-CI. That is, we will present the proportion of event observed before day t , for $t = 0, 1, 3, \dots$ for each treatment arm and the corresponding exact binomial two-sided 95% CIs (computed using the `binom.test()` function of R). This simple analysis is planned because we expect no censoring.

Quantitative outcomes analyses via quantiles (Q). Outcomes E2, E8 and E9 are quantitative outcomes (duration). They will (also) be analyzed by estimating the median within each treatment arm and their difference, together with two-sided 95%-CIs. The CI will be computed using non-parametric BCa Bootstrap (using $B=10,000$ replicates, via the R packages `boot` and `simpleboot`, see appendix 8.2 for the specific R code that we will use).

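### The reason given for ignoring the CRP randomisation stratum is specific to rare sequelae, yet the stratum is also ignored for durations and possibly common outcomes; if CRP is prognostic, their difference intervals are somewhat too wide

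*SAP*

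**What the plan says.** Section 3.2: "Randomization was stratified by C-reactive protein", with a cut at 35 mg/L.

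Section 6.1.1, on the primary analysis: "Note that the above statistical analyses will ignore that the randomization was stratified by C-reactive protein". It concedes: "This is usually not recommended, as this usually leads to a decrease in power". The defence is that this trial is a special case, "as we expect close to zero sequelae in each group". Two consequences are drawn from that premise: the power loss should be negligible, and type I error would be hard to control with an adjusted method.

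Section 6.2: the secondary analysis "will be similar to that of the primary outcome defined in Section 6.1.1", apart from a two-sided interval, no p-value and a different analysis set. Section 6.3, on binary outcomes S1-S3 and E3-E7: "They will be analyzed using the same statistical method as for the primary outcome", again with a two-sided interval and no p-value.

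For E2, E8 and E9, section 6.3 and appendix 8.2 bootstrap the difference in medians from two arm vectors that carry no CRP variable. For E1, appendix 8.4 stratifies the bootstrap by arm only. Section 4.1 limits all non-primary reporting to estimates with 95% intervals. No separate reason is given for ignoring the stratum in these analyses.

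**The concern.** The SAP accepts the general rule that an analysis should respect the randomisation strata, and claims an exception. The exception rests on a feature of one endpoint. A duration has no near-zero event count, so the premise has no meaning for E1, E2, E8 or E9. For S3, E6 and E7 it may or may not hold. The type I error argument does not carry over either, since none of these outcomes is tested.

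Stratified randomisation balances CRP between arms. If CRP predicts the outcome, the between-stratum spread largely cancels in the arm difference, but an unstratified interval still counts it. CRP is plausibly prognostic for E8, because the shift to follow-up treatment depends partly on falling CRP, and so for E2, which is E8 plus E9. For these outcomes the interval is the whole result, so what is at stake is precision.

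**Working it through.** **The plan's own figure.** The SAP states no precision for secondary or tertiary outcomes. Its only figures are primary-endpoint power in section 7, and they reproduce. The asymptotic formula gives Φ(0.05/√(2×0.99×0.01/81) − 1.96) = 89.2% (stated as about 90%). The exact score-ordered test gives 51.5%, 68.3% and 81.9% at risks of 1%, 0.5% and 0.25% (stated as 51%, 68% and 82%).

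**Inputs.** From the SAP: 1:1 allocation, two CRP strata, 90 per arm. Assumed, because the SAP gives none: half the children in each stratum, and the stratum risks and medians below.

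**Binary outcomes.** With stratum risks pL and pH and p̄ their mean:
- variance counted by the unstratified interval: T = p̄(1 − p̄)
- variance left after stratified allocation: W = [pL(1 − pL) + pH(1 − pH)]/2
- excess width = √(T/W) − 1

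| pL vs pH | T | W | Excess width |
|---|---|---|---|
| 0.5% vs 1.5% | 0.0099 | 0.009875 | 0.1% |
| 2% vs 8% | 0.0475 | 0.0466 | 1.0% |
| 5% vs 15% | 0.0900 | 0.0875 | 1.4% |
| 20% vs 40% | 0.2100 | 0.2000 | 2.5% |
| 10% vs 30% | 0.1600 | 0.1500 | 3.3% |
| 10% vs 40% | 0.1875 | 0.1650 | 6.6% |
| equal risks | T | T | 0 |

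The half-width is 1.96√(2V/90), with V set to T or W. At 20% vs 40% it falls from 13.4 to 13.1 percentage points. At 10% vs 40% it falls from 12.7 to 11.9.

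**Median differences.** These were simulated: log-normal durations with log-SD 0.5, 90 per arm, balanced within stratum, no treatment effect, 1,000 trials, percentile bootstrap with 300 resamples. Mean interval width in days:

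| Stratum medians (days) | Resampled by arm | By arm and CRP | Excess |
|---|---|---|---|
| 3 vs 3 | 1.109 | 1.105 | 0.4% (noise) |
| 3 vs 4 | 1.337 | 1.297 | 3.1% |
| 3 vs 5 | 1.643 | 1.498 | 9.7% |
| 3 vs 6 | 2.015 | 1.715 | 17.5% |

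With CRP prognostic, the arm-only interval covered about 97-98% instead of 95%. Truncating durations at a 3-day minimum gave similar excess widths. Resampling within arm and stratum kept coverage near 95%. The point estimate is the same under both schemes.

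**Limits of the simulation.** It uses percentile rather than BCa intervals and has no censoring, so it indicates the size for E2, E8 and E9 and only the direction for E1.

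**The case against.** The strongest reply is that the loss is conditional, small and safe. The SAP gives neither an event rate nor a CRP effect for any secondary or tertiary outcome. At 20% vs 40% only 0.3 percentage points of half-width are at stake. The intervals over-cover, so no false claim follows. One exact method with guaranteed coverage for all binary outcomes is a defensible choice. All of this stands, and it is why the point is minor.

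The link from CRP to the durations is also looser than it first looks. E8 depends on a fall in CRP together with clinical improvement and a minimum of 3 days, whereas the stratum is the baseline level. The planned length of follow-up treatment, and so most of E9 and much of E2, is set by type of infection. A CRP effect is plausible for E8 and unproven elsewhere.

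Two remedies that come to mind have real faults. A stratum-weighted difference of medians is a different estimand from the one planned. Choosing exact or stratified methods by observed event counts makes the method depend on the data. Neither is proposed here.

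The reply does not explain why a reason tied to rare sequelae should govern durations.

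A reader might infer more than the SAP supports:
- **That the primary analysis should be stratified.** At sequelae-like risks the excess is about 0.1%, so the SAP's reasoning holds there.
- **That all secondary and tertiary intervals are needlessly wide.** This fails without a CRP effect. Some outcomes, perhaps recurrence, S1, E3 or E5, may be rare enough for the same excuse.
- **That per-arm results suffer.** Between-stratum spread is a genuine part of how one arm's result varies, and it cancels only when balanced arms are compared. Per-arm risks, curves and medians are outside this point.

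**Conclusion.** The point holds as a gap in justification with a modest, conditional cost. The SAP's only reason for ignoring CRP cannot apply to E1, E2, E8 and E9, and may not apply to outcomes such as S3, E6 and E7.

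If CRP is prognostic, the affected between-arm intervals are conservative. They are about 1-3% too wide for binary outcomes with moderate CRP effects, about 7% at 10% vs 40%, and about 3-17% for median differences with stratum medians 1-3 days apart. If CRP is not prognostic, nothing is lost. These sizes rest on assumed equal strata, 90 per arm and assumed stratum risks and medians.

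Severity is minor: the error is in the safe direction and no formal test depends on it.

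**What to change.** - **E1, E2, E8, E9.** Keep the marginal difference in medians as the estimand, and resample within arm by CRP stratum for its interval. In appendix 8.4, set `strata` to the arm-by-CRP combination. In appendix 8.2, replace the two-vector call with the equivalent stratified one. Use this run for the difference only; 8.4 takes the per-arm medians from the same bootstrap object, so keep the arm-only run for those.
- **Sequelae and binary outcomes named in advance as rare.** Keep the exact unstratified method.
- **Binary outcomes named in advance as common.** Report a CRP-stratified Mantel-Haenszel risk difference with a stratified score 95% interval. The list must be fixed in the SAP and not depend on observed event counts.

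The cost is a short change of wording and a few lines of code, since the stratum was needed to randomise. The downside is that the interval for the common binary outcomes becomes asymptotic rather than exact. If the unstratified analyses are kept, section 6.3 should give a reason that fits these outcomes.

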6.3 Tertiary (safety and exploratory) Endpoints Analysis

We will also analyze the following Safety (**S**) and Exploratory (**E**) outcomes listed below. The information in parenthesis at the end of the description of each outcome refers to the statistical methods that will be used to analyze them, which is described below. Note that S1–S3 and E1–E5 were already listed in Table 1 in the protocol paper [11].

S1: severe complications during antibiotic treatment within 28 days. E.g., need for intensive care, septic shock, organ failure, pyomyositis, endocarditis, deep venous thrombosis. (**B + TTE**)

S2: need for surgical intervention during antibiotic treatment within 28 days; excluding diagnostic surgical intervention (diagnostic joint aspiration or diagnostic bone biopsy). (**B + TTE**)

S3: non-severe treatment-related adverse events within 3 months. E.g., complications of intravenous access (infection, need for replacement, extravasation) and drug side effects reported by medical staff, patients or parents (electronic questionnaire). (**B + TTE**)

E1: time from initiation of antibiotic treatment to apyrexia within 28 days, as reported by the patients or parents. Apyrexia will be defined by a temperature $< 38^{\circ}\text{C}$ for 24 hours. Patients or parents were asked to report the temperature three times per day (until apyrexia). (**KM**)

E2: total duration of antibiotic therapy within 3 months. (**Q + TTE**)

E3: sequelae within 12 months. E.g., abnormal mobility and growth abnormalities, assessed by clinical examination by a qualified pediatrician 12 months after the initiation of treatment, accepted range 11–14 months. (**B**)

E4: radiological abnormalities within 12 months. It is assessed by a qualified radiologist 12 months after initiation of treatment, accepted range 11–14 months. (**B**)

E5: secondary infection with antimicrobial-resistant organisms or *Clostridioides difficile*, within 3 months. (**B**)

E6: discontinuation of the randomized treatment strategy within 28 days. (**B + TTE**)

E7: early termination of falsely included patient within 6 months (i.e., suspicion of infection is abandoned). (**B + TTE**)

E8: time to shift to 'follow-up treatment' after clinical improvement (pain and mobility) and paraclinical improvement (decreasing C-reactive protein) within 3 months. (**Q + TTE**)

E9: duration of 'follow-up treatment' within 3 months (Note: E8+E9= E2). (**Q + TTE**)

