Kaplan-Meier analysis (KM). Outcome E1 is a time-to-event outcome (time to apyrexia). It will not be fully observed for all patients due to missing data, which will lead to censored observations. Hence we will use the Kaplan-Meier method to compute the “survival curves” for the event “apyrexia” within each group. We will define the time to apyrexia as the time to the third consecutive recording (observed or imputed) with a temperature $< 38^{\circ}\text{C}$ (i.e., approximately 24h with a temperature below 38°C). Missing temperature recordings will lead to imputation or censoring as follows. Last observation carried forward will be applied to impute up to two consecutive missing temperature recordings. If more than two consecutive recordings are missing, we will censor the

time to apyrexia at the time of the third consecutive missing temperature (the first time three consecutive temperatures are missing, if this happens several times). The `prodlim` package of R will be used to compute the Kaplan-Meier curves in each arm with pointwise two-sided 95%-CI. The corresponding median survival time in each arm and their difference will also be computed, also with two-sided 95%-CI, computed using non-parametric BCa Bootstrap (using $B=10,000$ replicates, via the R packages `boot` and `prodlim`, see appendix 8.4 for the specific R code that we will use).

Further remarks: for the outcome E6 (discontinuation of the randomized strategy), data about the reason for discontinuation have been collected. Additional (post hoc) exploratory analyses of these additional data will be performed too.

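### In E1, carried-forward temperatures can complete the run of three readings below 38°C, so apyrexia may be recorded even though the next observed reading is febrile

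*SAP*

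**What the plan says.** The outcome list in SAP section 6.3 gives the clinical definition of E1: "Apyrexia will be defined by a temperature" under 38°C lasting 24 hours. The data source is self-report: "Patients or parents were asked to report the temperature three times per day (until apyrexia").

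The Kaplan-Meier paragraph of the same section makes this operational. The event is "the time to the third consecutive recording (observed or imputed) with a temperature" below 38°C, which the SAP equates with roughly 24 hours. Missing values are expected: "It will not be fully observed for all patients due to missing data, which will lead to censored observations". For short gaps, "Last observation carried forward will be applied to impute up to two consecutive missing temperature recordings". For longer gaps the time is censored at the third missing reading, taking "the first time three consecutive temperatures are missing, if this happens several times".

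The analysis reports a Kaplan-Meier curve and median per arm, and the difference in medians with a two-sided 95% confidence interval. No sensitivity analysis is specified for E1.

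**The concern.** The event needs three readings and two of them may be imputed, so a single observation can be enough. The rule looks only backwards: nothing requires the completing reading to be observed, sets a minimum number of observed readings, or compares the imputed values with the first observed reading after the gap. Once the event is recorded, a later observed fever cannot undo it.

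At stake is whether an E1 event means what the outcome definition says, and whether the medians and their difference depend on how completely families reported temperatures.

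**Working it through.** **Inputs.** From SAP section 6.3: run length 3, longest imputed gap 2, censoring at the third consecutive missing reading, three readings per day. Even 8-hour spacing is an assumption.

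**Minimum number of observations per event.** 3 − 2 = 1.

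**Applying the rule by hand.** M is a missing reading. The phrase on imputing up to two readings can be taken gap-wise (a gap is filled only if its whole length is at most two) or sequentially (the first two values of any gap are filled).

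| Readings in order | SAP rule | Neighbour rule (see fix) |
|---|---|---|
| 39.0, 37.5, M, M, 39.0, 39.0, 37.5, 37.4, 37.3 | event at reading 4 | event at reading 9 |
| 39.0, 37.5, 37.4, M, 39.0, 39.0, 37.4, 37.3, 37.2 | event at reading 4 | event at reading 9 |
| 39.0, 37.5, M, 39.0, 39.0, 37.4, 37.3, 37.2 | event at reading 8 | event at reading 8 |
| 39.0, 37.5, M, M, 37.4, … | event at reading 4 | event at reading 4 |
| 39.0, 37.5, M, M, M, 39.0, … | sequential: event at reading 4; gap-wise: censored at reading 5 | censored at reading 5 |

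The first two rows show the defect, and it arises under both readings of the text. The SAP event comes 9 − 4 = 5 readings early, or 5 × 8 = 40 hours at even spacing. The third row shows that a lone afebrile reading must be followed by two missing ones. The last row shows that the text does not settle long gaps.

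**How often, first simulation (assumed inputs).** Three readings per day for 28 days, fever probability falling around day 3, readings independent, missingness at random, gap-wise reading, 20,000 children per setting:

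| Readings missing | Events resting on one observed reading | Events completed on an imputed value, next observed reading febrile | Both |
|---|---|---|---|
| 5% | 0.5% | 1.7% | 0.2% |
| 10% | 2.0% | 3.2% | 0.7% |
| 20% | 7.3% | 6.9% | 2.6% |
| 30% | 13.6% | 10.0% | 4.8% |

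**Other fever patterns (assumed).** Exponential fever duration with mean 2.5 or 4 days. While fever lasts, the chance of a febrile reading in the three daily slots is 0.35/0.6/0.9 or 0.8/0.8/0.9; a strictly monotone pattern was also run.

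- With 10–30% missing, about 1–11% of events under the fluctuating patterns end on an imputed value with the next observed reading febrile. Under monotone fever there are none.
- With 20% missing, 0–23% of events come earlier than with complete readings and 14–19% come later.
- Medians mostly move by 0–8 hours. The largest shift is 64 − 48 = 16 hours, at 30% missing under the sequential reading.

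**The case against.** The rule is explicit, prespecified and reproducible, and it openly counts imputed readings. E1 is one of nine exploratory outcomes, carries no hypothesis test and has no bearing on the non-inferiority conclusion. All of that stands and limits the weight of the point.

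A febrile next reading does not by itself make an event false: three observed afebrile readings followed by fever would also be an event. The percentages above therefore count events that the observed data do not support, and some of them would be events with complete data too.

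A reader might also infer three stronger conclusions that the document does not support:

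- **That the rule shortens time to apyrexia.** It also carries febrile values forward, which delays events. Under monotone fever with 20% missing, no event is early and 18–19% are late. Without a missingness rate or a known fever pattern, the net direction is open.
- **That only children whose last reading was febrile (or who have none) can be censored.** This follows only from the sequential reading. Under the gap-wise reading, 37.5 followed by three missing readings is censored with an afebrile last value; in runs with 20% missing, 14–41% of censored children had one.
- **That differential reporting will create a difference between arms.** The trial is open-label and temperatures are self-reported, so this is possible. But the SAP does not say which children are at home or in hospital, or that reporting differs by arm.

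**Conclusion.** The defect is real and follows from the wording alone: an imputed value may complete the run, and an observed fever straight after the gap is ignored. Such an event does not meet the definition given for E1 in the same section, and nothing else in the SAP corrects it.

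The frequency rests on assumed fever patterns and random missingness. It is a few percent of events at 10% missing, up to about 11% at 30%, and zero if fever never fluctuates. The effect on medians is probably small and its sign is unknown. The point is worth correcting because the correction is cheap; it does not threaten the trial's main result.

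**What to change.** Amend the Kaplan-Meier paragraph of section 6.3 as follows:

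1. Count a gap of one or two missing readings as below 38°C only when the observed readings on both sides are below 38°C.
2. Otherwise let the gap break the run and continue follow-up. Do not censor there. Censoring at the last observed reading would censor 61–81% of children at 20% missing and make medians 8–24 hours too short.
3. Keep censoring for gaps of three or more, and state that no value inside such a gap is imputed, so that it cannot create an event.
4. Report per arm the number of events that used any imputed reading, and keep the current rule as a sensitivity analysis.

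The cost is revised wording and a small change to the derivation. In the assumed settings at 20% missing, 5–9% of children are censored, against 3–9% under the current rule, and some medians come up to about 8 hours later. Reports were requested only until apyrexia, so some children will stop after one or two afebrile readings. They would be censored, not counted as events; this is a change only if the SAP intends the sequential reading, because the gap-wise reading censors them already.
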